Purpose	The primary purposes of the study are (1) to provide salvage therapy for individuals who previously participated in a peanut immunotherapy trial but did not demonstrate clinically significant desensitization, (2) to investigate the safety and tolerability of the salvage therapy regimen including both peanut flour and peanut flour equivalent, and (3) to explore mechanisms responsible for long-term desensitization and/or tolerance to food allergens induced by immunotherapy.
Study Design	This uncontrolled, observational, prospective, open-label study will be used to assess the safety and tolerability of a two-stage salvage therapy regimen: (a) peanut oral immunotherapy (OIT) followed by (b) extended maintenance with a peanut food equivalent.
Participants	We will enroll up to 100 eligible subjects who (1) did not demonstrate clinically significant desensitization in previous peanut immunotherapy trials, or (2) previously endured an extended time on placebo therapy, or (3) previously developed desensitization and then subsequently lost this protection due to time off from therapy.
Choice of Sample Size	The choice of sample size is based entirely on the ethical necessity of providing therapy to a pre-defined number of

	individuals in need of salvage therapy. We anticipate that up to 100 eligible subjects will be enrolled to receive the salvage therapy treatment regimen.
Study Duration	Approximately 12 months for each participant.
Primary Outcomes	
 Overall incidence rate of adverse events (including both AEs and SAEs) during the entire 2-stage treatment sequence Overall number of days of treatment missed during the entire 2-stage treatment sequence
Secondary Outcomes	
 Stage-specific incidence rate of all adverse events Days of treatment missed during each stage of treatment. Overall incidence rate of gastrointestinal AEs during the entire 2-stage treatment sequence. Overall incidence rate of Epipen use Overall incidence rate of drop-outs due to gastrointestinal AEs during the entire 2-stage treatment sequence.
Exploratory Measures	
 Changes in basophil, T cell, and antibody responses in peripheral blood and saliva samples (to explore the mechanisms responsible for long-term desensitization and/or tolerance to food allergens induced by immunotherapy.)

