In many current studies of peanut OIT, subjects are initially desensitized and then subsequently asked to avoid peanut for a discrete amount of time in order to assess the durability of the desensitization effect (sustained unresponsiveness). This research is critical to understanding the clinical and immunologic changes induced by peanut OIT and longer term implications of therapy. However, in the course of these investigations, the potential exists for subjects to lose their desensitization to peanut and their protection against accidental exposures to peanut.

The majority of current studies of OIT utilize a placebo group, some for extended periods of time (> 1 year). These extended placebo courses are vital to understanding the efficacy of OIT as up to 20% of peanut-allergic patients are thought to naturally develop tolerance to peanut. These subjects are not thought to be at any higher risk than those who are strictly avoiding peanut which is the current standard of care. However, concerns remain with withholding potentially protective treatment for these extended periods of time.

The use of investigational drugs to induce and maintain desensitization has been and continues to be the subject of numerous ongoing studies. However, there has been growing interest in the use of food products to maintain this effect with the thought that these readily available foods may allow for superior compliance. The safety and compliance with transitioning to a non-drug equivalent amount of peanut food has not been well studied.

The goals of this study protocol are several-fold. First and foremost, we would like to provide a salvage therapy option for those previously involved in vital peanut allergy research. Simultaneously, we will address three research aims:

Aim 1 --Investigate the safety and compliance in the 2-stage protocol in subjects who either (a) have previously developed desensitization and then subsequently lost this protection due to a period of time off of therapy or (b) have previously endured an extended time on placebo therapy.

Aim 2 -- Characterize and compare the two stages of the protocol in terms of safety and compliance.

Aim 3 -- Explore the mechanisms responsible for long-term desensitization and/or tolerance to food allergens induced by immunotherapy.

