10. STATISTICAL CONSIDERATIONS AND ANALYSIS STRATEGY

A. INTERIM AND FINAL ANALYSES

An interim analysis will be performed when at least 50 patients have finished their peanut OIT treatment phase and at least 25 patients finished 6 months of food equivalent treatment phase.

The interim analysis and the final analyses will include all subjects in the study who provided complete follow up information regarding their

compliance and adverse events, and will also include those who dropped out or were withdrawn from the study before its completion.

The final analyses will be performed when all subjects have completed the study.

B. PLANS FOR EACH SPECIFIC AIM

Aim 1. Investigate the safety and compliance in the 2-stage protocol in subjects who either (a) have previously developed desensitization and then subsequently lost this protection due to a period of time off of therapy, or (b) have previously endured an extended time on placebo therapy.

We will rely on the following methods to accomplish Aim 1:

1. Our primary analysis will focus on estimates of incidence rates of adverse events and the proportion of days of treatment missed during the treatment protocol.
2. Our secondary analyses will include estimation of
 - the overall incidence rate of gastrointestinal AEs during the entire 2-stage treatment sequence.
 - the overall incidence rate of Epipen use
 - the overall incidence rate of drop-outs due to gastrointestinal AEs during the entire 2-stage treatment sequence.
3. Exploratory analyses will be used to investigate potential candidate risk factors for AEs (using logistic regression models) and causes of missed treatment days (using generalized log-linear models for counts of days).
4. Descriptive tabular and graphical methods will be used to visualize the data and examine the relationships among the measures of interest using graphical and descriptive methods.

All statistical estimates will be tabulated with the corresponding 95% confidence intervals (CI). Interpretation of these CIs will be an integral part of the analyses. For Aim 1 (and for all the aims) sensitivity analyses will be performed to evaluate the robustness of the main results to reasonable perturbations of the choices of statistical methods and statistical assumptions used. For example, the influence of any extreme or questionable data value will be explored. Results of the sensitivity analyses will only be used to guide our level of confidence in the main results.

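### Does Aim 1, by naming two of the three enrolled groups, leave the primary analysis population unsettled?

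*Combined protocol and SAP*

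**What the plan says.** The synopsis describes the participants as those who "1) did not demonstrate clinically significant desensitization in previous peanut immunotherapy trials, or (2) previously endured an extended time on placebo therapy", and adds a third group: people who had become desensitized and lost that protection while off therapy. Its first stated purpose is "to provide salvage therapy for individuals who previously participated in a peanut immunotherapy trial but did not demonstrate clinically significant desensitization".

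Aim 1 is worded almost identically in sections 1.B and 10.B. It concerns "subjects who either (a) have previously developed desensitization and then subsequently lost this protection due to a period of time off of therapy" or, as group (b), those with an extended time on placebo. No third group is listed. Item 1 under Aim 1 in 10.B is the only analysis called primary: "Our primary analysis will focus on estimates of incidence rates of adverse events and the proportion of days of treatment missed".

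Section 10.A opens its rule on who is analysed with "The interim analysis and the final analyses will include all subjects in the study who provided complete follow up information regarding their" (the two items being adherence and safety events). It then adds people who left early, whether by their own choice or the investigator's. The sentence does not mention prior-trial group.

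**The concern.** The primary analysis sits under an aim whose stated population is narrower than the enrolled one. A literal reader would restrict it to groups (a) and (b); a reader of 10.A would not. The subjects in dispute include those around whom the synopsis words its first purpose.

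This is a single-arm estimation study, so its main results are the rates and their 95% confidence intervals. If the population were truly open, an investigator with open-label data could choose it after seeing results, and the overall and stage-specific estimates could describe different people. The boundary of group (b) is also loose. Section 1.B says only that "The majority of current studies of OIT utilize a placebo group, some for extended periods of time (> 1 year"), which describes other studies and does not define an extended course here.

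**Working it through.** The plan gives no figure to reproduce: the sample size of up to 100 is set on ethical grounds, with no split by group. The check is mainly a comparison of texts.

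**1. Where prior-trial groups appear, and where they do not.**
- Synopsis, Purpose (1): non-desensitized subjects only.
- Section 1.B, Rationale: lost-protection and extended-placebo subjects, singled out as of special interest.
- Synopsis, Participants: all three groups.
- Aim 1 in 1.B and 10.B: the same two groups as the Rationale.
- Section 4.A, inclusion criteria: no groups. The test is completion of a peanut immunotherapy trial within 18 months and inability to tolerate 300 mg or more.
- Section 3.A, primary objective: patients from peanut immunotherapy research, undivided.
- Section 3.B, primary and secondary outcomes: no groups.
- Section 10.A, analysis set: no groups.
- Section 10.B, Aim 2: no groups.

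**2. Which text sets the analysis population.** Only 10.A says who is included, and it covers the interim and final analyses alike. It does condition on follow-up information, and it adds dropouts and withdrawals. That is a separate matter from prior-trial group. No text says that an enrolled subject is to be left out because of an earlier trial.

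**3. Can the group lists be exclusions?** Suppose every list restricted what follows from it. Purpose (1) would then remove the lost-protection subjects, and Aim 1 would remove the active-treatment non-responders. Applied together, they would leave only extended-placebo subjects who were never desensitized. Aim 2 would meanwhile use everyone, so the overall rate from Aim 1 would not correspond to the stage-specific rates from Aim 2. Nothing in the plan suggests that this is meant. Read as descriptions of whom the study is chiefly for, the lists are compatible with each other and with 10.A.

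**4. Who would drop out on the literal reading.** The groups overlap, since a subject long on placebo may also count as not desensitized. The omitted set is therefore smaller than the first synopsis group. It consists mainly of actively treated non-responders, plus any placebo subject whose course was not extended.

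**5. Illustration only.** Let s be the share of subjects in the omitted set and r their adverse event rate relative to the others, with equal follow-up. Neither is in the documents; s = 0.05 to 0.30 and r = 0.5 to 2 are assumed.
- Subjects kept out of 100: 100(1 − s) = 95 to 70.
- Interval width ratio when r = 1: 1/√(1 − s) = 1.026 to 1.195, with no shift in the rate.
- Restricted rate relative to the all-subject rate, minus 1: 1/[1 + s(r − 1)] − 1.
  - r = 0.5: 1/0.975 − 1 = +2.6% and 1/0.85 − 1 = +17.6%.
  - r = 2: 1/1.05 − 1 = −4.8% and 1/1.30 − 1 = −23.1%.

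These figures show what the literal reading could do under assumed inputs. They do not show that the plan adopts it.

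**The case for a change.** The strongest reply is that the two-group wording appears in both 1.B and 10.B, so it is hardly a one-off slip, and that it heads the very block containing the primary analysis. Even if 10.A governs, the pooled estimate then describes more people than Aim 1 names. In an estimation study the population is part of the result, and rewording costs little. Section 1.B also hopes that the data will help identify high-risk groups, yet no planned table or model names prior response to immunotherapy.

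The mismatch in wording stands, and a report should say plainly whom the estimates cover. The rest carries less weight. The repetition is explained by 1.B, which gives special attention to exactly those two groups before stating the aims. On high-risk groups, 1.B speaks of guiding future research and promises no subgroup analysis. The exploratory models name no risk factor at all, so prior history is not singled out for omission, and analysts remain free to include it.

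A required table by prior-trial category would need arm, placebo duration and response recorded at entry, which the inclusion criterion does not demand. It would also be imprecise. With an assumed 20 events in a category, the exact Poisson 95% limits are 12.22 and 30.89, or 0.61 and 1.54 times the estimate; repeated events in the same subject would widen them further. Such a table is a reasonable option for description, but its absence is not a defect.

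**Conclusion.** The inconsistency is real but clerical. Section 10.A settles the population without regard to prior-trial group, and the objective, outcomes and Aim 2 agree with it. An analyst following the plan would pool all three groups, and matching the words of Aim 1 to 10.A would change no estimate or interval. No error rate is at risk, because no hypothesis test or success criterion is attached to these estimates.

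The conclusion rests on reading Aim 1 as a statement of interest rather than an exclusion, which the text of 1.B supports. It would fail only if the investigators did intend to omit prior non-responders, and nothing in the documents says so. How far results would then move cannot be derived from the documents.

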3. OBJECTIVES AND OUTCOME MEASURES

A. OBJECTIVES

1. The primary objective of this study is to place patients who have been involved in peanut immunotherapy research on salvage therapy while investigating safety and compliance of oral immunotherapy and food equivalent therapy in these patients.
2. The secondary objectives include:
 - a. Investigation of incidence of gastrointestinal adverse event, drop outs, and Epipen use.
 - b. Investigation of the compliance of participation with peanut OIT and peanut food equivalent

B. OUTCOME MEASURES

1. Primary Outcomes
 - Overall incidence rate of adverse events (including both AEs and SAEs)

during the entire 2-stage treatment sequence (OIT followed by peanut containing food equivalent)

- Overall number of days of treatment missed during the entire 2-stage treatment sequence

2. Secondary Outcomes

- Stage-specific incidence rate of all adverse events
- Days of treatment missed during each stage of treatment.
- Overall incidence rate of gastrointestinal AEs during the entire 2-stage treatment sequence.
- Overall incidence rate of Epipen use
- Overall incidence rate of drop-outs due to gastrointestinal AEs during the entire 2-stage treatment sequence.

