6. The participant experiences severe symptoms during the build-up or maintenance phases as a result peanut OIT dosing

7. In the investigator's discretion, there is poor compliance or any other concern that would create an unacceptable risk to the subject.

8. The participant dies.

9. The study ends.

To the extent possible, participants who discontinue therapy will be followed to observe and record study outcomes.

D. STUDY TERMINATION CRITERIA

If any of the stopping rules listed below are met, study enrollment will be suspended, the initial dose escalation phase and build-up phase will be stopped, and all enrolled participants will remain on their current dose pending expedited review of all pertinent data by the Data Safety Monitoring Board:

1. Any death related to peanut OIT dosing.
2. More than one event comprising systemic allergic symptoms with significant hypotension at any stage of the protocol.
3. More than 3 participants require more than 2 injections of epinephrine during dosing of the peanut product.
4. More than 3 of the following events:
 - Severe adverse event, other than anaphylaxis, related to investigational product.
 - Eosinophilic esophagitis.

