4. MAINTENANCE PHASE

After completing build up phase to 300 mg study protein, the subjects will continue to receive their maintenance dose of study protein daily for the proceeding 3 months of the study (maintenance phase). After 3 months of maintenance, the subject may have mechanistic studies done at end of study visit. Data from our previous studies indicate that home dosing is safe, with infrequent

reactions which are typically mild. These data have identified several risk factors for reactions, which include dosing on an empty stomach, fever/illness, and activity/exercise shortly before or after dosing. Families of subjects will be asked to administer the study protein with additional food such as at snack or meal times, and will be instructed to hold the dose during illness and contact study personnel for instruction. After 3 months of daily maintenance peanut protein OIT, subjects will have a follow up visit where they are assessed by study investigator and if qualified they will be switched to food equivalent of peanut protein for the following 6 months.

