8. SAFETY MONITORING

A. DEFINITIONS

Adverse Event (AE) or Medical Event

An adverse event is a new, undesirable medical event or occurrence or worsening of an existing condition (including an abnormal laboratory finding) in a subject that occurs during the study, whether or not it is considered to be study related. Adverse events or medical events and toxicities are treatment emergent signs and symptoms.

Serious Adverse Event (SAE)

A serious adverse event is defined as any adverse therapy experience occurring at any dose that suggests a significant hazard, contraindication, side effect, or precaution. This includes, but may not be limited to any of the following events: (This terminology is from Section B.2 on the FDA MedWatch form. For a copy of the current MedWatch Form 3500, see the list of PDF forms on the Web at <http://www.fda.gov/opacom/morechoices/fdaforms/cder.html>)

- 1) Death: A death occurring during the study or which comes to the attention of the investigator during the protocol-defined follow-

up after the completion of therapy whether or not considered treatment-related, must be reported.

- 2) Life-threatening: Any adverse therapy experience that places the subject or subjects, in the view of the investigator, at immediate risk of death from the reaction as it occurred (i.e., it does not include a reaction that, had it occurred in a more serious form, might have caused death)
- 3) In-patient hospitalizations.
- 4) Persistent or significant disability or incapacity.
- 5) Congenital anomaly/birth defect.
- 6) An event that required intervention to prevent permanent impairment or damage

Unexpected Adverse Events

An adverse event is considered “unexpected” when its nature or severity is not consistent with the descriptions in the protocol or informed consents.

For subjects who become pregnant during the study and whom we will withdraw from the study as stated above, we will continue to monitor them with phone calls every 3 months until delivery. We will use our phone interview questionnaire to report any adverse outcomes for these subjects and report the outcome of all pregnancies in our study report.

B. TOXICITY GRADING

Symptoms associated with systemic allergic reactions and/or anaphylaxis that occur during administration of peanut flour or peanut equivalent food will be graded according to table below, that was adapted from the grading of allergic reactions in the following article:

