Aim 2. Characterize and compare the two stages of the protocol in terms of safety and compliance.

We will rely on the following methods to accomplish Aim 2:

1. Our main analyses will focus on stage-specific estimates of incidence rates of adverse events and the proportion of days of treatment missed.

Comparisons of the two stages will rely on logistic regression models for rates, and generalized log-linear models for counts of days. The primary emphasis will be on point estimates and confidence interval estimates. No hypothesis tests will be performed.

2. Our secondary analyses will include estimation of

- the stage-specific incidence rates of gastrointestinal AEs during the entire 2-stage treatment sequence.
- the stage-specific incidence rates of Epipen use
- the stage-specific incidence rates of drop-outs due to gastrointestinal AEs.

Comparisons of the two stages will rely on logistic regression models for rates, and generalized log-linear models for counts of Epipen usages. The primary emphasis will be on point estimates and confidence interval estimates. No hypothesis tests will be performed.

3. Exploratory analyses will be used to investigate potential candidate risk factors for AEs (using logistic regression models) and causes of missed treatment days (using generalized log-linear models for counts of days).

4. Descriptive tabular and graphical methods will be used to visualize the data and examine the relationships among the measures of interest using graphical and descriptive methods.

Statistical estimates of interest include stage-specific parameter estimates (e.g., incidence rates) as well as estimates of differences between stage-specific parameters (e.g., odds ratios, or rate differences). All statistical estimates will be tabulated with the corresponding 95% confidence intervals (CI). Interpretation of these CIs will be an integral part of analysis. For Aim 2, sensitivity analyses will be performed to evaluate the robustness of the main

results to reasonable perturbations of the choices of statistical methods and statistical assumptions used.

Aim 3. Explore the mechanisms responsible for long-term desensitization and/or tolerance to food allergens induced by immunotherapy.

We will rely on the following methods to accomplish Aim 3:

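### The primary AE rate and its stage comparison have no exposure term, so for dosing-related events they can shift with compliance and drop-out at unchanged risk per dose

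*Combined protocol and SAP*

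**What the plan says.** The Synopsis gives the first primary outcome as "Overall incidence rate of adverse events (including both AEs and SAEs) during the entire 2-stage treatment sequence", and Section 3.B repeats it. The second primary outcome is the number of treatment days missed. For the analysis, Section 10.B (Aim 1, item 1) states: "Our primary analysis will focus on estimates of incidence rates of adverse events and the proportion of days of treatment missed". Nowhere is the denominator of the AE rate fixed as participants, calendar days, days on treatment or doses taken.

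For Aim 2, Section 10.B states: "Comparisons of the two stages will rely on logistic regression models for rates". Log-linear models are named for counts of missed days and of Epipen uses. No offset or other exposure term is given for any of these models.

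The numerator is all-cause: Section 8.A counts an AE "whether or not it is considered to be study related".

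The plan creates three kinds of untreated time:

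- **Held doses.** Under Section 5.D.4, families "will be instructed to hold the dose during illness and contact study personnel for instruction".
- **Missed doses.** Section 5.F lets participants with gaps in dosing stay in the study.
- **Time after stopping.** Section 4.C states: "To the extent possible, participants who discontinue therapy will be followed to observe and record study outcomes". Section 10.A keeps drop-outs and withdrawn participants in the analyses.

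No section says whether any of this time counts towards the AE rate. The sensitivity analyses in 10.B are described in general terms and do not mention exposure.

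**The concern.** A reaction to a study dose needs a dose. If time without dosing enters the estimate, the rate of dosing-related AEs falls as doses are missed, although each dose carries the same risk. Safety and compliance are the study's two headline results, and Aim 2 compares flour with food on both, so part of the safety contrast may only restate the compliance contrast.

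Drop-out works the same way. A participant who stops during the flour stage and is followed to month 12 would, if later days count, add only untreated time to the food stage.

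**Working it through.** The plan has no figure to reproduce. Section 10.C sets the sample size (up to 100) on ethical grounds, and no AE rate, compliance level or drop-out rate is given. Every rate and fraction below is an assumption; only the stage lengths (up to 6 months of flour, then 6 months of food, Section 7.E) come from the documents.

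**Notation.** b = background AE rate per day; r = dosing-related AE rate per dosed day; m = fraction of days with no dose. The rate per calendar day is b + r(1 − m).

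**1. All AEs dosing-related (b = 0), equal risk per dose.** The food:flour ratio is (1 − m_food)/(1 − m_flour).

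| Missed on flour | Missed on food | Apparent food:flour ratio |
|---|---|---|
| 5% | 15% | 0.85/0.95 = 0.89 |
| 5% | 20% | 0.80/0.95 = 0.84 |
| 15% | 5% | 0.95/0.85 = 1.12 |
| 20% | 5% | 0.95/0.80 = 1.19 |

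With doses taken as the denominator, the ratio is 1.00 in every row.

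**2. With background AEs (b = 0.03, r = 0.02).** Flour at 5% missed: 0.03 + 0.02 × 0.95 = 0.049. Food at 20% missed: 0.03 + 0.02 × 0.80 = 0.046. The ratio is 0.046/0.049 = 0.94, against 0.84 without background events.

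**3. Drop-out, later days counted, dosing-related events only.**

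- If 20% stop at month 2 and are followed to month 12, the treated share of time is (0.8 × 12 + 0.2 × 2)/12 = 0.833, so the overall rate is understated by 17%.
- If 20% stop halfway through the flour stage, the treated share is 0.8 + 0.2 × 0.5 = 0.90 in the flour stage and 0.80 in the food stage. The apparent ratio is 0.80/0.90 = 0.89.

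**4. Rate read as the proportion of participants with at least one AE.** With risk p = 0.005 per dose and 182.5 days in a stage, the proportion is 1 − 0.995^(182.5(1 − m)). It is 59.9% with no doses missed and 51.9% with 20% missed. The per-participant reading that a logistic model suggests therefore shifts the same way.

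**5. Events that could offset the effect.** A 3-day gap at r = 0.05 removes 3 × 0.05 = 0.15 expected events. An extra risk of 0.15 on restarting would cancel that.

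**6. A doses-taken offset applied to all-cause AEs.** With the inputs of step 2, the ratio becomes (0.046/0.80)/(0.049/0.95) = 1.11 although the risk per dose is equal. The offset must match the type of event.

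**The case against.** The strongest reply is that the plan never says untreated days will count. The stated treatment sequence is a window of observation, not a denominator. Section 8.A describes AEs as treatment emergent, which favours counting on treatment, and logistic regression with odds ratios suggests a proportion of participants. This stands: a reader might infer that the plan puts missed, held and post-discontinuation days in the denominator, but the documents only leave the matter open.

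A reader might also infer that poorer compliance always makes a regimen or stage look safer. The documents do not support that either:

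- AEs are all-cause, and calendar time is a proper denominator for background events.
- Doses are held during illness, and the illness may itself be an AE, so held days can carry events.
- Restarting after a gap may carry extra risk, and Section 5.F has the PI or study team decide on dosing after longer gaps.
- Section 1.B suggests that compliance may be better on food. In that case food would look worse than flour, not better.

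Nor does the plan treat compliance as unconnected with safety. Missed days are reported beside the AE rate, overall and by stage, and 10.B plans to examine relationships among the measures. That lets a reader see poor compliance but does not correct the rate.

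Finally, the consequences are limited. The study is single-arm, Aim 2 has no hypothesis tests, the stopping rules in 4.D use event counts, and the DSMB receives listings. No stated safety decision uses this rate. It is still a primary result and the basis of the stage comparison.

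**Conclusion.** The concern holds in limited form. Neither the primary AE rate nor its stage comparison has an exposure term, so for dosing-related AEs both can shift with compliance and drop-out at unchanged risk per dose. With all AEs dosing-related and missed fractions of 5% against 15–20%, the apparent food:flour ratio lies between 0.84 and 0.89 or between 1.12 and 1.19, depending on which stage misses more. A large background share of AEs brings the first range close to 1 (0.94 in place of 0.84).

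The true size is unknown, because the documents give no compliance, AE or drop-out figures. A bias in one fixed direction is not established. A calendar-time rate is a legitimate summary if it is labelled as such and shown with a per-dose rate. The change is worth making because the choice of denominator is otherwise open until the data are seen, and the daily diary (5.G) and compliance sheets (6.F, continued in the food phase under 5.D.5) already record what is needed.

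**What to change.** 1. **Dosing-related AEs.** Define these in advance, either as reactions within the two-hour window that 5.G uses for reactions after eating peanut or as AEs judged associated with the study product under 8.C. Report them per 100 doses taken, from the daily sheets, overall and by stage. Compare stages with a log-linear count model with log(doses taken) as offset, for these events only.
2. **All-cause AEs.** Report a rate per person-time on treatment, from first dose to last dose plus a pre-stated window, and compare stages with a log(person-time) offset.
3. **Who counts when.** Count participants in the food stage only from their first food dose. Tabulate events after discontinuation separately.
4. **Missing sheets.** Report how many participants lack compliance sheets, and give a sensitivity analysis for unknown doses.

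No new data collection is needed. The cost is two denominators to present and a count model in place of logistic regression for AE rates; the plan already uses log-linear models for other counts. Dose counts will be incomplete for some drop-outs, because food-stage sheets are handed in only at the end of that phase.
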